7.5.2.2 Six Minute Walk Test

In Part I of the study, the 6MWT ([Solway et al. 2001](#)) will be administered at Baseline and the Part I Termination Visits to assess walking ability. For continuing subjects, the assessment at the Part I Termination Visit will serve as the baseline assessment for Part II of the study. In Parts II, III, and IV of the study, the 6MWT will be administered at Baseline (for treatment naïve subjects), Months 3, 6, 12, 18, 24, 30, 36 and Termination Visits. The 6MWT will be administered by a licensed physical therapist in accordance with American Thoracic Society (ATS) guidelines ([ATS 2002](#)). Blood pressure, heart rate and self-reported Borg scale dyspnea and fatigue ratings will be recorded before and after the test

administration. ATS guidelines require a subject to have a pre-test resting heart rate of less than 120 beats/minute, systolic blood pressure of less than 180 mm Hg and diastolic blood pressure of less than 100 mm Hg to ensure safety. Subjects who meet the safety criteria will be instructed to walk the length of a pre-measured 20 meter course for six consecutive minutes. Traffic cones will be used to standardize the distance in hallways longer than 20 meters. The subject will walk laps around the cones until the six minute time period has expired. However, the test will not be interrupted and the subject will continue to walk for the 6-minute duration of the test. Instructions and encouragement will be given according to the script provided in the ATS guidelines. The distance walked at the end of six minutes will be recorded in meters at the time of test administration. The percent of predicted normal values will be calculated after the testing using published normative data ([Gibbons et al. 2001](#)).

7.5.2.3 Walking Speed Test

In Part I of the study, the walking speed test will be administered at Baseline and the Part I Termination Visits to assess gait speed. In Parts II, III, and IV of the study, the walking speed test will be administered at Baseline (for treatment naïve subjects), Months 3, 6, 12, 18, 24, 30, 36 and Termination Visits. The test will be administered twice by a licensed physical therapist, once at a comfortable speed and once at a maximum speed. Subjects will be instructed to walk the length of a pre-measured 25 foot (7.62 meter) course. Traffic cones or tape on the floor will be used to standardize the distance. Subjects will have a few feet at the beginning and the end of the 25 foot course to allow for acceleration and deceleration. For the comfortable speed test, subjects will be instructed to walk at their normal pace. For the maximum speed test, subjects will be instructed to walk as fast as they safely can without running. The total number of seconds required to complete the test for each speed will be recorded in seconds at the time of test administration. Subject performance relative to peers will be calculated after the testing using published normative data ([Bohannon 1997a](#)).

7.5.2.4 Weighted Arm Lift Test

In Part I of the study, the weighted arm lift test ([Agarwal et al. 2006](#)) will be administered at Baseline and the Part I Termination Visits, to assess upper limb function. In Parts II, III, and IV of the study, the weighted arm lift test will be administered at Baseline (for treatment naïve subjects), Months 3, 6, 12, 18, 24, 30, 36 and Termination Visits. The test will be administered by a licensed physical therapist. The subject will be asked to sit in a chair holding a 1 kg barbell with the shoulder adducted, the elbow in full flexion and the forearm in supination. On command, the subject will be asked to lift the arm above the head until the elbow is fully extended, then to lower the arm back to the starting position. The subject will be asked to repeat the action at a comfortable pace according to their own rhythm for the 30 second duration of the test. The test will be performed bilaterally and the final score will be the mean of the total number of completed repetitions from both arms. The number of completed repetitions from each arm and the mean score will be recorded at the time of test administration.

7.5.2.5 HIBM Functional Activities Scale

In Part I of the study, the HIBM Functional Activities Scale (HIBM-FAS) will be administered at the Baseline and Part I Termination Visits, to assess functional disability. For continuing subjects, the assessment at the Part I Termination Visit will serve as the baseline assessment for Part II of the study. Additional HIBM-FAS assessments in Parts II, III, and IV of the study will be performed at Baseline (for treatment naïve subjects), Months 6, 18, 36 and Termination Visits. The scale is being developed specifically for patients with GNE myopathy (HIBM) based on feedback received from affected individuals on the impact of the disease on their function. Items in the scale assess the subject's ability to independently perform various activities of living that involve self-care, mobility and use of the upper and lower extremities. The scale will be administered in an interview format by a licensed physical therapist and scored after the testing.

7.5.3 Exploratory Efficacy Measures

Additional novel exploratory biomarkers of sialylation and muscle injury may also be evaluated to explore the possible best methodology to monitor GNE Myopathy disease. Candidate biomarkers present in serum may include:

- CK levels
- Neural cell adhesion molecule (NCAM) measured using an ELISA assay and/or immunoblot assay to characterize the NCAM types present.
- Other biomarkers of muscle injury and remodeling, including MMP9 and microRNAs

Assessment of serum protein markers will only be conducted in Part I of the study. In Parts II, III, and IV of the study, CK levels will be the only exploratory efficacy measure assessed.

7.5.4 Safety Measures & General Assessments

7.5.4.1 Medical History

For continuing subjects, the medical history information obtained during the UX001-CL201 study will carry over to this study. A detailed medical history, including a GNE Myopathy-specific medical history, will be obtained at Screening/Baseline Visit for new subjects entering the study (i.e. treatment naïve individuals). The medical history will solicit information on any prior or existing medical conditions that might interfere with study participation or safety. This medical history should elicit all major illnesses, diagnoses, and surgeries to date.

7.5.4.2 Interval History

Each interval history is intended to record any signs, symptoms, or events (e.g., falls) experienced by the subject since the prior study visit that are not related to study procedure(s) performed at prior study visits or study drug. Interval history may include exacerbation or

improvement in existing medical conditions (including the clinical manifestations of GNE Myopathy) that might interfere with study participation, safety, and/or positively or negatively impact performance of functional assessments. Interval history may identify under-reported AEs, and will be collected at the study visits indicated in the Schedule of Events ([Table 2.1](#) and [Table 2.2](#)).

7.5.4.3 Vital Signs

Vital signs will include seated systolic blood pressure and diastolic blood pressure measured in millimeters of mercury (mm Hg), heart rate in beats per minute, respiration rate in breaths per minute, and temperature in degrees Celsius (°C). Vital signs measurements will be performed at study visits indicated in the Schedule of Events ([Table 2.1](#) and [Table 2.2](#)).

7.5.4.4 Height and Weight Evaluations

Measurements of height and weight will be collected on each subject using a stadiometer and a scale by the physical therapist administering the performance testing. Height and weight data will be used to evaluate each subject's muscle strength and function using published normative data where available.

7.5.4.5 Physical Examination

In Part I of the study, complete physical examinations will be performed at the Baseline and Part I Termination Visits. For continuing subjects, findings in the Part I Termination Visit will serve as the Part II baseline assessment. In Parts II, III, and IV of the study, a complete physical examination will be performed at Baseline (for treatment naïve subjects), Months 6, 18, 36 and the Termination Visits. Physical examinations will include assessments of general appearance; head, eyes, ears, nose, and throat; the cardiovascular, dermatologic, lymphatic, respiratory, gastrointestinal, genitourinary, musculoskeletal, neurologic systems (at designated visits where a complete neurological examination is not performed).

Other body systems may be examined and symptoms of increasing muscle weakness and pain will be recorded. The presence of changes in muscle pain or weakness should be evaluated carefully by a complete neurologic exam when these changes are reported by subjects. The specific muscle location and pain should be noted. Clinically significant changes from Baseline will be recorded as AEs.

7.5.4.6 Neurological Examination

In Part I of the study, a neurological examination will be performed at the Baseline and Part I Termination Visits. For continuing subjects, findings in the Part I Termination Visit will serve as the Part II baseline assessment. In Parts II, III, and IV of the study, a neurological examinations will be performed at Baseline (for treatment naïve subjects), Months 6, 18, 36 and the Termination Visits. The neurological examination will include assessments of cognition, cranial nerves, motor function, coordination and gait, reflexes, and sensory function.

7.5.4.7 Clinical Laboratory Tests

The clinical laboratory evaluations to be performed in this study are listed in Table 7.5.4.7.1; the time points for these evaluations are indicated in the Schedule of Events ([Table 2.1](#) and [Table 2.2](#)). Fasting is not required. Refer to the central laboratory manual for additional details.

Table 7.5.4.7.1: Clinical Laboratory Assessments

Chemistry	Hematology	Urinalysis	Special Assessments
Alanine aminotransferase (ALT/SGPT)	Hematocrit	Appearance	Free serum SA
Alkaline phosphatase	Hemoglobin	Color	Serum pregnancy test (if positive urine pregnancy test)
Amylase	MCH concentration (MCHC)	pH	
Aspartate aminotransferase (AST/SGOT)	Mean corpuscular hemoglobin (MCH)	Specific gravity	
Bilirubin (direct and total)	Mean corpuscular volume (MCV)	Ketones	
Blood urea nitrogen (BUN)	Platelet count	Protein	
Calcium	Red blood cell (RBC) count	Glucose	
Chloride	Reticulocyte count	Bilirubin	
Cholesterol (total)	WBC differential	Nitrite	
Creatine kinase (CK)	Neutrophil count (absolute and %)	Urobilinogen	
Creatinine	Lymphocyte count (absolute and %)	Hemoglobin	
Gamma-glutamyl transpeptidase (GGT)	Monocyte count (absolute and %)	Creatinine	
Glucose, non-fasting	Eosinophil count (absolute and %)		
Lactate dehydrogenase (LDH)	Basophil count (absolute and %)		
Lipase	White blood cell (WBC) count		
Phosphorus			
Potassium			
Protein (albumin and total)			
Sodium			
Triglycerides			

Subjects who experience a SAE possibly or probably related to study drug or other AE of concern may, at the discretion of the investigator (and/or medical monitor), have additional blood samples taken for safety laboratory tests.

7.5.4.8 Adverse Events

All AEs will be recorded from the time the subject signs the informed consent until 30 days after the last dose of study drug or, if applicable, until the date the subject signs the informed consent for the open-label extension study, UX001-CL302, whichever occurs sooner. The determination, evaluation, reporting, and follow-up of AEs will be performed as outlined in Section 8.5. At each visit subjects will be asked about any new or ongoing AEs since the previous visit. Assessments of AEs will occur at every study visit.

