Evaluations of safety, changes in clinical endpoints such as muscle strength, mobility, and function, and changes in exploratory serum biomarkers will be performed according to the Schedule of Events specific to each phase of the study ([Table 2.1](#) and [Table 2.2](#)). A Termination Visit will be conducted 4 weeks after subjects receive their last dose of study drug (last dose of study drug received at Month 36). For subjects who are eligible and choose to participate in the UX001-CL302 open-label extension study, the Month 36 Visit is considered the end of study visit and the Termination Visit is not required. Any subject who discontinues the current study early or is ineligible or decides not to participate in the UX001-CL302 open-label extension study is required to have a Termination Visit 4 weeks after their last dose of study drug, as per Schedule of Events. Efficacy data analyses will be conducted at the end of the Treatment Period, although interim analyses may be performed at the discretion of Ultragenyx.

Safety will be monitored throughout the study based on physical examinations, clinical laboratory analyses, and reporting of adverse events (AEs) and Serious Adverse Events (SAEs). An independent Data Monitoring Committee (DMC) will review safety information periodically on an ad hoc basis as outlined in the DMC charter, which is maintained separately from this protocol.

NUMBER OF SUBJECTS PLANNED:

Up to 46 subjects previously treated in the UX001-CL201 study will be enrolled. Approximately 10 subjects, naïve to SA and MaNAc treatment, will be enrolled directly into Part II of the study.

DIAGNOSIS AND CRITERIA FOR INCLUSION AND EXCLUSION:

Individuals eligible to participate in this study must meet all of the following criteria:

- Enrollment in, and successful completion of the UX001-CL201 protocol **OR**
(for 10 treatment naïve subjects):
 - Have a confirmed diagnosis of GNE Myopathy
 - Aged 18 -65 years of age, inclusive
 - Able to walk ≥ 200 meters and < 80% of predicted normal during the 6MWT (orthotics and assistive devices allowed)
 - No prior history of treatment with SA or MaNAc
- Must be willing and able to provide written, signed informed consent after the nature of the study has been explained, and prior to any research-related procedures
- Must be willing and able to comply with all study procedures
- Sexually active subjects must be willing to use an acceptable method of contraception while

participating in the study

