7.3.3 Removal of Subjects from Therapy or Assessment

In accordance with the Declaration of Helsinki, subjects have the right to withdraw from the study at any time for any reason. The principal investigators and Ultragenyx also have the right to remove subjects from the study. Subjects may be removed from the study for the following reasons:

- Occurrence of an unacceptable AE
- An illness that, in the judgment of the principal investigator or Ultragenyx, might invalidate the study or place the subject at risk
- At the request of the subject, principal investigator, or Ultragenyx, whether for administrative or other reasons
- Protocol deviation or unreliable behavior

If the reason for removal of a subject from the study is an AE, the AE and any related test or procedure results will be recorded in the source documents and transcribed onto the Case Report Form (CRF). Each clinically significant abnormal laboratory value or other clinically meaningful abnormality should be followed until the abnormality resolves or until a decision is made that it is not likely to resolve. If such abnormalities do not return to normal within 30 days after the last dose given, their etiology should be identified and Ultragenyx should be notified. All unscheduled tests must be reported to Ultragenyx immediately.

If a subject discontinues from the study prematurely, every reasonable effort should be made to perform the (Early) Termination Visit procedures within four weeks of discontinuation.

Subjects who withdraw or are removed from the study after receiving study drug may not re-enter the study.

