8.5.4 Adverse Event Reporting to Ultragenyx

8.5.4.1 General

All AEs (i.e. any new or worsening in severity or frequency of a preexisting condition) with onset after the subject signs consent for study participation must be promptly documented on the AE eCRF via the EDC system. The Principal Investigator is responsible for evaluating all AEs, obtaining supporting documents, and ensuring documentation of the event is adequate. Details of the AE must include severity, relationship to study drug, duration, and outcome.

All AEs will be collected from the time the subject signs the informed consent through 30 days following the last dose of study drug, or, if applicable, until the date the subject signs the informed consent for the open-label extension study, UX001-CL302, whichever occurs sooner. In addition for those subjects choosing not to enroll in UX001-CL302, the Investigator should report any AE that occurs more than 30 days following the last dose of study drug that is believed to have a reasonable possibility of being associated with study drug.

AEs ongoing after the defined follow-up period stated in the paragraph above should have a comment in the source document by the Investigator that the event has recovered, recovered with sequelae, or stabilized.

8.5.4.2 Serious Adverse Events, Serious Adverse Drug Reactions, and Requirements for Immediate Reporting

Any SAE that occurs at any time during the study, including a clinically significantly abnormal laboratory test result that is considered serious, must be reported within 24 hours of knowledge of the event to Ultragenyx or its designee. These requirements apply equally to all subjects, regardless of the study phase or the at-risk subject's treatment assignment or dosage. The reporting requirement for SAEs is from the time of signing of the ICF through 30 days following the last study drug administration.

SAEs will be reported by completing and submitting SAE report forms to Ultragenyx or its designee. Initial SAE reports must be followed by detailed descriptions. These should include copies of hospital case records and other documents when requested. Follow-up SAE information must be submitted in a timely manner as additional information becomes available. All SAEs regardless of relationship to study drug must be followed to resolution or stabilization if improvement is not expected.

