6.5.3 Derived Safety, Dosing, and Medication Variables

Non Treatment Emergent Adverse Events (AEs) include all adverse events that stopped the day prior to the start of study medication, started prior to the start of study medication but did not increase in severity or relationship during treatment, or started more than 30 days after the final study medication dosing date. In this study there is no expectation on non-treatment emergent adverse events in any subjects who roll-over from UX0010-CL201. Subjects in the treatment naïve population may have non-treatment emergent adverse events recorded if an event occurs between screening (informed consent) and the first dose of planned study medication (12g.day SA-ER/SA-IR).

Treatment Emergent Adverse Events (TEAE) include all adverse events that start on or after the first dose of study medication, or adverse events that are present prior to the first dose of study medication, but their severity or relationship increases after the first dose of study medication up to and including 30 days after the final study medication dosing date.

Dosing: Number of doses administered will be calculated for each subject by summing the number of doses administered over all visits.

Medications:

Prior medications include all medications that are taken prior to the first dose of study medication date.

Concomitant medications include all medications that are taken on or after the date of first dose of study medication.

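### CL202 recording of non-serious AEs ends when the CL302 consent is signed, even for a subject still on CL202 drug or later found ineligible

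*Protocol*

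**What the plan says.** - **AE recording (Protocol 7.5.4.8 and 8.5.4.1).** Section 8.5.4.1 states: "All AEs will be collected from the time the subject signs the informed consent through 30 days following the last dose of study drug". Both sections then add an alternative end point: "until the date the subject signs the informed consent for the open-label extension study, UX001-CL302, whichever occurs sooner". Section 7.5.4.8 also has AEs assessed at every study visit.
- **Late reports (Protocol 8.5.4.1).** "In addition for those subjects choosing not to enroll in UX001-CL302, the Investigator should report any AE that occurs more than 30 days following". Those days are counted from the final dose, and the duty applies where a link to study drug is reasonably possible.
- **SAEs (Protocol 8.5.4.2).** "The reporting requirement for SAEs is from the time of signing of the ICF through 30 days following the last study drug administration". CL302 is not mentioned. Deaths (8.5.4.2), urgent safety issues (8.5.4.3, 8.5.4.4) and pregnancies (8.5.4.5) are also covered to day 30 with no CL302 cut-off.
- **Termination Visit.** The Synopsis says that anyone who stops early or is "ineligible or decides not to participate in the UX001-CL302 open-label extension study is required to have a Termination Visit" four weeks after the last dose. Section 7.1 and Table 2.2 footnote c agree. Section 7.5.1 names early termination and declining CL302, but leaves out ineligibility.
- **Analysis (SAP 6.5.3).** An AE counts as treatment-emergent "up to and including 30 days after the final study medication dosing date", with no CL302 exception.

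**The concern.** A safety window should follow exposure. Here one of its two end points is an administrative act in another study. Nothing in the protocol says when CL302 consent is signed, and nothing makes the cut-off depend on the last CL202 dose, confirmed CL302 eligibility or a first CL302 dose.

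Two kinds of subject are exposed to this. One signs before the last CL202 dose and is still taking CL202 drug after CL202 AE recording has closed. The other signs, fails CL302 eligibility and receives no further drug, so no CL302 treatment period takes over.

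Safety objectives are listed first in Protocol Section 6, and the study plans only about 46 + 10 = 56 subjects. A few unrecorded events could therefore change an incidence table. The SAP would also count treatment-emergent AEs over days on which the protocol no longer records non-serious ones, and the tables would not show this.

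**Working it through.** No power or alpha figure is involved. The check is date arithmetic and a comparison of sections.

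**1. The stated rule.** Let day 0 be the last CL202 dose and *c* the day on which CL302 consent is signed.

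- End of AE recording (7.5.4.8, 8.5.4.1) = min(30, *c*)
- End of SAE reporting (8.5.4.2) = 30
- End of treatment-emergent window (SAP 6.5.3) = 30

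If CL302 consent is never signed, all three give day 30 and the sections agree.

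**2. Effect of the signing day.** The documents give no value for *c*, so the values below are assumptions that show the range.

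| Signing day *c* | AE recording ends | On-drug days outside, max(0, −*c*) | Post-dose days outside, 30 − max(0, min(30, *c*)) | SAE and SAP windows end |
|---|---|---|---|---|
| −14 | −14 | 14 | 30 | 30 |
| 0 | 0 | 0 | 30 | 30 |
| +7 | +7 | 0 | 23 | 30 |
| +28 | +28 | 0 | 2 | 30 |
| +30 or later | +30 | 0 | 0 | 30 |

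Day 0 is a natural case, because the Synopsis and Sections 7.1 and 7.5.1 place the last dose at Month 36 and the Synopsis makes that the final visit for rollover subjects. For a true rollover, the post-dose days may be days on CL302 drug. For a signer who never enters CL302, they are ordinary post-treatment follow-up.

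**3. The signer found ineligible.** Suppose consent is signed on day 0 and ineligibility is established afterwards.

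- Sections 7.5.4.8 and 8.5.4.1: AE recording closed on day 0.
- Synopsis, Section 7.1, Table 2.2 footnote c: Termination Visit due at 4 × 7 = day 28.
- Section 7.5.4.8: AEs are assessed at that visit, 28 days after recording closed.
- Late-report sentence in 8.5.4.1: limited to "for those subjects choosing not to enroll in UX001-CL302, the Investigator should report any AE". An ineligible subject has not made that choice, so the sentence does not clearly apply.
- Section 8.5.4.2: an SAE on any of days 1 to 30 is still reportable, while AE recording is closed.

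These provisions cannot all be followed as written.

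**4. Contact at the end of the window.** The nominal Termination Visit on day 28 comes 30 − 28 = 2 days before the window ends, and no contact is scheduled at or after day 30. This does not close the window, which is defined by date.

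**The case against.** The strongest reply is that the cut-off is a hand-over. CL202 collects AEs from its own consent (7.5.4.8, Table 2.2 footnote h). If CL302 does the same, events after the signature are captured there, perhaps even for signers later found ineligible. That is plausible and would remove most of the loss for true rollovers, but the CL302 protocol is not among the documents. Even if it is so, an event on CL202 drug after an early signature would sit in CL302's data and not in CL202's record.

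Other replies also stand:

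- Only non-serious AEs are affected. SAEs, deaths, urgent safety issues and pregnancies stay reportable to day 30.
- For rollovers the protocol takes the earlier of two dates, so it never promised a full 30 days of non-serious AE recording.
- The SAP mismatch is partly a matter of versions. SAP Section 1 cites the original protocol and Amendment 1, and CL302 came in a later amendment. SAP 6.5.3 also classifies events; it does not commit anyone to collect them.

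A reader might infer two stronger points that the documents do not support. The first is that a visit before day 30 defeats the 30-day window, or that the Termination Visit timings contradict each other. The window runs by date from the last dose. A visit at four weeks satisfies both the four-week rule and the request in Section 7.3.3 for "Termination Visit procedures within four weeks of discontinuation". The second is that AEs are selectively lost in subjects who stop early. CL302 is offered to subjects who complete CL202 (Synopsis; Table 2.2 footnote k), so the consent cut-off should not reach early discontinuers. Section 7.3.3 also requires clinically meaningful abnormalities to be followed until they resolve or are judged unlikely to.

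**Conclusion.** The point holds as a defect in a stated rule. Followed literally, Sections 7.5.4.8 and 8.5.4.1 leave non-serious AEs outside CL202 recording for anyone who signs CL302 consent while on CL202 drug, or who signs and does not enter CL302. For the ineligible signer the rule conflicts with the required Termination Visit and with AE assessment at every visit. For anyone who signs before day 30 it differs from the SAE and SAP windows.

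Per subject, between 0 and 30 post-dose days are affected, plus every on-drug day after an early signature. The number of subjects affected is unknown: both situations are possible under the text, but neither is described. Actual loss of events depends on CL302's AE rules, which cannot be checked here. The missing contact at day 30 is a minor addition, with a nominal gap of 2 days. The wording should be corrected, but no broader failure of safety follow-up is shown.

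**What to change.** 1. In Protocol 7.5.4.8 and 8.5.4.1, end CL202 AE collection at the first dose taken under CL302, or 30 days after the last CL202 dose if no CL302 dose has been taken by then.
2. Use the same end point in Protocol 8.5.4.2 and SAP 6.5.3. For rollovers this shortens the present CL202 SAE window, so first confirm that CL302 reports SAEs from its first dose at the latest. If it does not, keep the 30 days in 8.5.4.2.
3. Extend the late-report sentence in 8.5.4.1 to every subject who does not receive CL302 drug, including those found ineligible, and add ineligibility to the Termination Visit rule in 7.5.1.
4. Optionally, where the last visit falls before day 30, close the window with one of the additional telephone contacts that Table 2.2 footnote j already permits.

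The cost is wording in two documents and, for some subjects, one call. The downside is that events between CL302 consent and the first CL302 dose may be recorded in both studies and would need de-duplication.
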